## 14.2. Statistical early stopping rule

The rate of deaths from cancer will be checked and an early stopping rule is defined on this criteria according to a sequential method (A Kramar, C Bascoul-Mollevi, 2009), used to recommend the stop of inclusions if the rate of deaths from cancer is significantly over 5% after 12 months of following, with a nominal alpha at 10% and gamma parameter at 4 for the inclusion of the 51 planned patients.

These statistical early stopping rule will be applied from the second cancer death until the 5th.

Simulations are summarized in the following table:

The maximum acceptable percentage of death from cancer at 1 year	Number of death from cancer leading to inclusion stop	Number of inclusions
4%	2	9
	3	20
	4	30
	5	39
5%	2	6
	3	16
	4	25
	5	33
6%	2	5
	3	13
	4	21
	5	29

The maximum acceptable percentage of deaths from cancer at 12 months was fixed at 5% according to literature data.

The interruption of inclusions is recommended if the second death from cancer occurred among the first 6 patients, the 3rd among the first 16 patients, the 4th among the first 25 patients and the 5th among the first 33 patients. Beyond the second death from cancer, regardless of the number of patients included a meeting of the Supervisory Committee of the trial will be scheduled to discuss how to continue this trial.

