## SYNOPSIS

TITLE	RE-IORT 01 : FEASIBILITY CLINICAL TRIAL OF INTRAOPERATIVE RADIOTHERAPY (IORT) AND A SECOND BREAST-CONSERVING SURGERY AFTER LOCAL RECURRENCE OF BREAST CARCINOMA
PROTOCOL ACRONYM:	RE-IORT 01
STUDY SPONSOR	ICM - Institut régional du Cancer Montpellier Contact name: [name] [name] – France
STUDY COORDINATOR	[name] [name] Institut régional du Cancer Montpellier Radiation Oncology Department ICM Montpellier [name] France /France [contact] [contact] [contact]
CLINICAL RESEARCH ASSOCIATE	[name] Institut régional du Cancer Montpellier Clinical and Translational Research Department [contact] [contact] [contact]
BIOSTATISTICIAN /DATAMANAGER	[name] / [name] Institut régional du Cancer Montpellier Methodology and Data Management Center [contact] [contact] Mail : [contact] [contact]
CLINICAL RESEARCH PHARMACOVIGILANT	[name] Institut régional du Cancer Montpellier Clinical Research Pharmacovigilance Unit Phone: [name] [contact] Mail: [contact]
Design	Phase II single arm multicenter trial design to evaluate the feasibility of a second breast-conserving surgery combined with re-irradiation using IORT after local recurrence of breast carcinoma. 65 patients are scheduled.
Rational	Currently, the rate of ipsilateral breast tumor recurrence (IBTR) after breast-conserving surgery and radiotherapy remains at 10% at 10 years to 15% at 20 years, respectively. IBTR is an independent predictor of poor survival with a 3 to 4.6 increased risk of cancer-related death.  In a heterogeneous population, local control remains a major therapeutic challenge for these relapses, especially those considered of better prognosis, namely occurring late and of low histological grade. Therapeutic de-escalation is possible for these relapses to avoid a mutilating and often traumatic mastectomy.  However, this second conservative surgery has a high rate of second local

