STATISTICAL CONSIDERATIONS	
Sample size calculation
 
The primary endpoint is the success rate at 12 months, the success being defined as no grade <math>\geq 2</math> fibrosis according to NCI-CTCAE V4.0 classification.
 
A success rate of 95% is expected. The sample size calculation is based on:
 
 
• The Fleming one-stage design with one-sided alpha=0.05 and beta=0.05.
 
• <math>p_0 = 80\%</math> (success rate at 12 months, threshold below which we will consider the Intraoperative Radiotherapy toxicity as unacceptable, assuming 20% failure)
 
• <math>p_1 = 95\%</math> (success rate target at 12 months)
 
 
A total of 46 evaluable patients is required; taking into account un-evaluable patients, the number of subjects is adjusted to 65
 
It should be noted that the alpha level is set at 5% (one-sided), risk of concluding as to efficacy (<math>p > p_0</math>) whereas there is no efficacy (<math>p \leq p_0</math>), and the beta level is set at 5%, risk of concluding as to the absence of efficacy (<math>p < p_1</math>) whereas there is noteworthy efficacy (<math>p \geq p_1</math>)
 
After inclusion of 46 evaluable patients (at least 3 assessments within 12 months), it will be possible to conclude that the study demonstrates inefficacy if the success number is less than or equal to 40, or efficacy if the success number is greater than or equal to 41.
 
The patient size and the decision rule are presented here-below:
 
  
 Hyp	Rate of success at 12 months	<math>p_0</math>	<math>p_1</math>	Fleming one stage design*	N total	
   
 Rate		80	95	(46, <math>\leq 40</math>, <math>\geq 41</math>)	65	
  
 
*(N, n1, n2)
	Hyp	Rate of success at 12 months	$p_0$	$p_1$	Fleming one stage design*	N total	Rate		80	95	(46, $\leq 40$ , $\geq 41$ )	65
Hyp	Rate of success at 12 months	$p_0$	$p_1$	Fleming one stage design*	N total								
Rate		80	95	(46, $\leq 40$ , $\geq 41$ )	65								

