### **The study is planned to enroll 65 patients.**

The patient must provide a signed informed consent form prior to any study related procedure. The principal measured outcome will be the cutaneous fibrosis rate 12 months after treatment. We considered that a rate of 20% or more of Grade  $\geq 2$  fibrosis would be unacceptable.

All patients will be followed for:

- Survival and local breast control after this study treatment for an extended carcinologic follow-up.

- Toxicities during and after treatment (3, 6, 12 and 24 months after IORT and each year during 3 years)
- Survival follow-up will be done every 3, 6, 12 and 24 months after IORT and each year during 5 years by clinical visits unless death lost to follow-up or withdrawal of consent.

The survival follow-up period will continue for 3 years after the last patient was included in the study.

The end of study (last patient last visit) will occur after all patients have completed their last assessment.

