### 14.1. Sample size calculation

The primary objective is to evaluate the success rate at 12 months, defined as the non-observation of fibrosis at 12 months after IORT.

A success rate of 95% is expected. The sample size calculation is based on:

- The Fleming one-stage design with one-sided alpha=0.05 and beta=0.05.

- $p_0 = 80\%$  (success rate at 12 months, threshold below which we will consider the Intraoperative Radiotherapy toxicity as unacceptable, assuming 20% failure)
- $p_1 = 95\%$  (success rate target at 12 months)

A total of 46 evaluable patients are required; taking into account non-evaluable patients (postoperative histological results that do not meet the inclusion criteria or less than 3 assessments before 12 months), the number of subjects is adjusted to 65.

It should be noted that the alpha level is set at 5% (one-sided), risk of concluding as to efficacy ( $p > p_0$ ) whereas there is no efficacy ( $p \leq p_0$ ), and the beta level is set at 5%, risk of concluding as to the absence of efficacy ( $p < p_1$ ) whereas there is noteworthy efficacy ( $p \geq p_1$ ).

After inclusion of 46 evaluable patients, it will be possible to conclude that the study arm demonstrates inefficacy if the success number is less than or equal to 40, or efficacy if the success number is greater than or equal to 41.

The sample size and the decision rule are presented here-below:

Hyp.	Rate of success at 12 months	$p_0$	$p_1$	Fleming one-stage design *	N total
Rate		80	95	(46, $\leq 40$ , $\geq 41$ )	65

\* (N,  $n_1$ ,  $n_2$ )

N = total sample size required.

$n_1$  = maximal number of success required to conclude => non-efficacy.

$n_2$  = minimal number of success required to conclude => efficacy.

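### Section 14.2 sets the cancer-death stopping rule for 51 planned patients, but the protocol plans 65 everywhere else; reconcile the number and rerun or confirm the table

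*Protocol*

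**What the plan says.** Section 14.2 sets a rule on deaths from cancer within 12 months, with a maximum acceptable rate of 5%, using a cited sequential method "with a nominal alpha at 10% and gamma parameter at 4 for the inclusion of the 51 planned patients". On its scope it adds: "These statistical early stopping rule will be applied from the second cancer death until the 5th". In the 5% row the stopping boundaries are the 2nd death among the first 6 patients, the 3rd among the first 16, "the 4th among the first 25 patients and the 5th among the first 33 patients". The same table has rows for limits of 4% and 6%. Section 14.2 also calls a meeting of the supervisory committee beyond the second cancer death, whatever the number included. Section 13 has the IDMC kept informed of cancer deaths under this rule.

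The planned size is given differently in four other places:

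- Synopsis, Design: "65 patients are scheduled".
- Synopsis, Statistical considerations: "A total of 46 evaluable patients is required; taking into account un-evaluable patients, the number of subjects is adjusted to 65".
- Section 6: "The study is planned to enroll 65 patients".
- Section 14.1: "A total of 46 evaluable patients are required", and, after allowing for non-evaluable patients, "the number of subjects is adjusted to 65".

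**The concern.** Section 14.2 lists 51 beside alpha and gamma, as one of the quantities the rule was set up with. It is neither the planned enrolment (65) nor the evaluable number (46), and nothing in the protocol presents it as a subset, a treated population or a superseded target. The sentence is intact and is current text.

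A sequential rule specified for a given number of inclusions should match the trial in which it is applied. If its spending depends on the fraction of planned inclusions, the boundaries depend on that total. Two questions are therefore open: why 51, and was the table left as it was when 65 became the plan? At stake are the stated basis of the safety rule that the IDMC will follow and, possibly, some of its boundary numbers.

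**Working it through.** **1. The numbers side by side**

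| Place in the protocol | Planned | Evaluable |
|---|---|---|
| Synopsis, Design | 65 | – |
| Synopsis, Statistical considerations | 65 | 46 |
| Section 6 | 65 | – |
| Section 14.1 | 65 | 46 |
| Section 14.2 | 51 | – |

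46/65 = 70.8%, so 65 allows for 29.2% non-evaluable patients. 46/51 = 90.2%, and 46 × 1.10 = 50.6, which rounds up to 51. So 51 could be 46 plus about 10%, but that is conjecture; the document does not say so.

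**2. Does the printed table perform differently at 51 and at 65?**

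Inputs from Section 14.2: the 5% row is (death, patients) = (2, 6), (3, 16), (4, 25), (5, 33); the 4% row is (2, 9), (3, 20), (4, 30), (5, 39); the 6% row is (2, 5), (3, 13), (4, 21), (5, 29).

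Assumption: each patient's 12-month cancer-death status is counted in order of inclusion, independently, with probability p. The trial stops when the k-th death falls among the first n_k patients. The probability is followed exactly, patient by patient: from d deaths, the next patient adds a death with probability p. That path stops if d + 1 = k and the patient's number is at most n_k; otherwise it continues.

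The first step can be checked by hand. P(at least 2 deaths in 6 at p = 0.05) = 1 − 0.95^6 − 6 × 0.05 × 0.95^5 = 0.0328.

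For the 5% row at p = 0.05, the stopping probabilities by boundary are:

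- 2nd death: 0.0328
- 3rd death: 0.0285
- 4th death: 0.0125
- 5th death: 0.0051
- Total: 0.0788

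| Row, at its own limit | N = 46 | N = 51 | N = 65 |
|---|---|---|---|
| 4% | 8.4% | 8.4% | 8.4% |
| 5% | 7.9% | 7.9% | 7.9% |
| 6% | 7.9% | 7.9% | 7.9% |

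The columns agree because the last boundaries (39, 33 and 29) all come before patient 46. For the same reason the 5% row stops with probability 35.8% at a true rate of 10%, and 67.2% at 15%, for all three sizes. The 10% and 15% rates are illustrative; they are not in the protocol.

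**3. Would a table derived for 65 differ?**

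The formula of the cited method is not in the protocol, so this can only be indicated. Assume spending f(t) = 0.10 × (1 − exp(−4t)) / (1 − exp(−4)), with t = inclusions/N. Take each boundary as the largest n whose added stopping probability stays within the spending since the previous boundary. For the first boundary of the 5% row:

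- N = 51: f(6/51) = 0.0382, which is at least 0.0328, so 6 is allowed. At 7 the probability is 0.0444 against f(7/51) = 0.0430, so 7 is not. Boundary 6.
- N = 65: f(6/65) = 0.0314, which is below 0.0328, so 6 is not allowed. At 5 the probability is 0.0226 against f(5/65) = 0.0270. Boundary 5.

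| Row | Printed | Assumed formula, N = 51 | Assumed formula, N = 65 |
|---|---|---|---|
| 4% | 9 / 20 / 30 / 39 | 9 / 21 / 31 / 41 | 8 / 21 / 32 / 43 |
| 5% | 6 / 16 / 25 / 33 | 6 / 17 / 26 / 34 | 5 / 16 / 26 / 35 |
| 6% | 5 / 13 / 21 / 29 | 5 / 14 / 22 / 30 | 4 / 13 / 22 / 30 |

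At N = 51 the first boundary matches in every row, and all 12 values lie within 2 patients of print. At N = 65 the first boundary misses in every row, and one value is off by 4 (43 against 39). The table therefore fits 51 better, as Section 14.2 itself says. No variant tried with the stated alpha, gamma and 51 matched all 12 printed values, so the sponsor's calculation is not reproduced here.

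Within the assumed formula, going from 51 to 65 moves each 5% boundary by at most one patient. The N = 65 set stops with probability 7.9%, 37.9% and 70.4% at true rates of 5%, 10% and 15%, against 7.9%, 35.8% and 67.2% for the printed row.

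**The case against.** The strongest reply is that nothing practical turns on 51 against 65. The printed boundaries behave identically at either size, their false-stop probability is under the nominal 10%, and an indicative rerun moves the 5% row by one patient at most. The text also says which size the table was set for. All of this stands, and it limits the weight of the point. It does not remove the contradiction: a stated parameter of a safety rule disagrees with the planned enrolment, and only the sponsor can say which is meant.

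Two stronger readings may tempt a reader. The first is that the wrong number makes the rule unusable or raises its error rate; the recursion shows that it does not. The second is that patients 34 to 65 (32 of 65, or 49%) are left without oversight because no boundary lies beyond patient 33. The document does not support this either. The rule is limited by design to the 2nd to 5th death, and a committee meeting is triggered beyond the second cancer death at any number of inclusions. Taking that as at least 3 deaths among 65 patients, the binomial probability is 96% at a true rate of 10%. Extending the boundaries, or using up the rest of the nominal 10%, would be a preference and not a correction.

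**Conclusion.** The contradiction is certain from the text alone: 51 in Section 14.2 against 65 in four other places, with no explanation. It should be corrected, because the protocol's only numerical stopping rule should be specified for the trial being run.

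Its numerical weight is small. On the assumption that 12-month status is counted in order of inclusion, the printed table remains usable and keeps its false-stop probability at 7.9% to 8.4%, whichever size applies. That a rerun for 65 would move the 5% boundaries by about one patient rests on an assumed spending function, and it is not a proposed table.

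**What to change.** In Section 14.2, reconcile 51 with 65, or explain what 51 refers to. Rerun the sponsor's own method with the stated 5% limit, alpha of 10% and gamma of 4 for the reconciled number. Then either confirm that the printed table holds, or replace it together with the sentence below it that repeats the boundaries.

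The cost is one corrected number, one run of existing software and possibly one replaced table and sentence. It needs no extra patients, visits or data.

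### The cancer-death stopping rule has no numerical boundary beyond the fifth death or beyond the first 33 patients, leaving later deaths to committee discretion; extending the table is a cheap improvement.

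*Protocol*

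**What the plan says.** Protocol section 14.2 defines an early stopping rule on deaths from cancer. The limit is explicit: "The maximum acceptable percentage of deaths from cancer at 12 months was fixed at 5% according to literature data". The design parameters are given as "with a nominal alpha at 10% and gamma parameter at 4 for the inclusion of the 51 planned patients". When a boundary is crossed, the rule recommends that inclusions stop.

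The boundaries at the 5% limit are "if the second death from cancer occurred among the first 6 patients, the 3rd among the first 16 patients", then "the 4th among the first 25 patients and the 5th among the first 33 patients". The range of application is closed at both ends: "These statistical early stopping rule will be applied from the second cancer death until the 5th". The table has no row for a sixth death under any of the three limits it shows (4%, 5%, 6%).

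Planned enrolment is 65. Section 6 says "The study is planned to enroll 65 patients", and section 14.1 says that, to allow for non-evaluable patients, "the number of subjects is adjusted to 65".

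Beyond the table, section 14.2 provides for a Supervisory Committee meeting once there are more than two cancer deaths, whatever the number included, and attaches no threshold to it. Section 13 has the IDMC regularly informed of cancer deaths under the same rule, allows it to advise stopping, and lets the sponsor consult it ad hoc. Section 11 (Trial Discontinuation) lets the steering committee close the study early on general grounds.

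**The concern.** The numerical rule ends at a fixed death count and a fixed patient number, both well short of full enrolment. Suppose that, after a first death at any earlier point, the second to fifth deaths fall at patients 7, 17, 26 and 34. Each misses its boundary by one patient, so no stop is recommended, although the observed rate is 5/34 = 14.7%. From that point no number of further deaths can trigger the numerical rule.

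The gap does not depend on which planned number is right. On the rule's own 51 patients, numbers 34 to 51 have no boundary; on the 65 planned, numbers 34 to 65 have none. At stake is how well the rule detects a cancer-death rate clearly above its own limit. The protocol does not state the rule's probability of stopping at any rate, so a reader cannot see what the early end costs.

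**Working it through.** **Inputs.** From section 14.2: limit 5%; nominal alpha 10%; gamma 4; 51 patients; boundaries (death k, by patient n) = (2, 6), (3, 16), (4, 25), (5, 33). From sections 6 and 14.1: 65 planned inclusions. Assumptions of this review: patients are independent, and each patient's 12-month cancer-death status is known in order of inclusion. True rates other than 5% are scenarios.

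**Coverage.** 51 − 33 = 18 patients (35%) on the rule's own number; 65 − 33 = 32 patients (49%) on planned enrolment.

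**Method.** Go through the patients one at a time, carrying the probability of each death count among paths not yet stopped. When the k-th death falls at patient i, stop if k is 2 to 5 and i ≤ n(k). The first boundary can be checked by hand at 5%:

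P(at least 2 deaths in 6) = 1 − 0.95^6 − 6 × 0.05 × 0.95^5 = 1 − 0.7351 − 0.2321 = 0.0328.

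**Comparison with the stated 10%.** Cumulative probability of crossing at a true 5%:

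| By patient | 6 | 16 | 25 | 33 | 65 |
|---|---|---|---|---|---|
| P(stop) | 3.3% | 6.1% | 7.4% | 7.9% | 7.9% |

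The 10% is not reached, and the curve is flat after patient 33. Simply adding the four marginal tail probabilities (3.3%, 4.3%, 3.4%, 2.3%) gives 13.3%, so that reading does not return 10% either.

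**How much of the shortfall is truncation.** The protocol does not give the spending function. If a Hwang-Shih-DeCani form with gamma 4 is assumed, the alpha allowed by patient 33 of 51 is

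0.10 × (1 − e^(−4 × 33/51)) / (1 − e^(−4)) = 9.4%.

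The stated boundaries use 7.9% by then, so part of the gap already exists before the rule ends. Under that assumption, boundaries built for 51 patients come within one or two patients of the stated four, so the table looks like a 51-patient design cut off at the fifth death.

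**Stopping probability, as written and extended.** The extension continues the table's spacing by hand (6th by 42, 7th by 50, 8th by 58, 9th by 65). It is illustrative and is not output of the cited method.

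| True rate | As written | Extended to 65 | Difference (points) |
|---|---|---|---|
| 5% | 7.9% | 8.5% | 0.6 |
| 10% | 35.8% | 44.4% | 8.6 |
| 15% | 67.2% | 81.6% | 14.4 |

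Extending only to 51 (6th by 42, 7th by 50) gives 8.4%, 42% and 77%. Other ways of completing the boundary, tried under the assumed spending form or by similar spacing, put the probability at a true 10% between 41% and 53%.

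**Undetected accumulation.** At a true 10% with 65 patients, the probability of six or more cancer deaths with no boundary crossed is 32%.

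**Inclusions avoided.** Mean number of the 65 not enrolled because of a stop: 18.2 as written against 19.6 extended at a true 10% (about 1.5 more), and 34.5 against 37.0 at 15% (2.5 more). On 51 patients the gain is 0.5 and 0.8.

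**The case against.** The strongest case against the point is that a limited rule followed by judgement is an open and coherent choice. The protocol sets no power requirement for this rule. Later deaths are not ignored: a committee meets once there are more than two, the IDMC is kept informed and may advise stopping, and the steering committee may close the study. In the example above, a committee is engaged before patient 34. A late boundary also does little, because the rule only stops inclusions: a crossing at the 65th patient spares nobody. This largely stands. It limits the benefit to a few patients and lowers the importance of the point. It does not supply a criterion, since none of those provisions says how many later deaths are too many.

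Three stronger readings are tempting and are not supported.

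- A reader might infer that the rule fails its 10% alpha because it ends early. The protocol calls 10% nominal, and spending less is conservative for false stops. The illustrative extension recovers only 0.6 of the 2.1-point gap.
- A reader might infer that patients 34 to 65 go unmonitored. They lack a numerical boundary, but the committee provisions still apply. Because deaths accrue over 12 months, a fifth death among the first 33 can also stop inclusions while later patients are being enrolled.
- A reader might attribute the whole 32 of 65 to the cut-off at the fifth death. Patients 52 to 65 are uncovered because the rule was sized for 51, which is a separate mismatch.

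**Conclusion.** The point holds in a limited form. Section 14.2 gives no numerical boundary for a fifth death after the first 33 patients or for any sixth or later death, so 18 of 51 or 32 of 65 patients depend on discretion alone once the table ends. As written, the rule stops with probability 7.9%, 36% and 67% at true rates of 5%, 10% and 15%, and at 10% there is a 32% chance of six or more cancer deaths without a crossing.

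These figures rest on independent patients whose 12-month status is known in order of inclusion; reporting delay could reduce the number of inclusions avoided. The 10% and 15% rates and the extended boundaries are this review's illustrations, and the cited method's own output may differ. Detection improves by roughly 9 to 14 points in the illustration, but the practical gain is modest, at about 1.5 to 2.5 inclusions of 65. This is a cheap improvement to consider and does not invalidate the rule.

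**What to change.** In section 14.2:

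1. Reconcile the 51 patients used for the rule with the 65 planned in sections 6 and 14.1.
2. Remove the restriction that ends the rule at the fifth death.
3. Rerun the same method with the same limit, nominal alpha and gamma, and tabulate a boundary for each further death up to the last planned inclusion. If the planned number changes, the first four boundaries may move too.
4. State the resulting probability of stopping at true rates of 5%, 10% and 15%, and the assumption about when 12-month status is known.

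The 5% limit and the committee provisions stay as they are. The cost is one rerun of the sponsor's program, a longer table and, in the illustration, about 0.6 points more risk of a false stop at a true 5% (7.9% to 8.5%), still under the nominal 10%.
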